8.2.11 Nursing/Patient Implications

- Assess labs prior to administration (esp. CBC, platelet count, BUN, Cr.).
- Assess urine output prior to each dose. Maintain hydration. Urine output should be 100-150 ml/hr. Diuretics may be ordered.
- Administer antiemetics before cisplatin. Post-treatment antiemetics should be given as per institutional guidelines.
- Observe carefully for signs of anaphylaxis.
- Monitor for signs of neurotoxicity, hearing loss.

8.3 Carboplatin

8.3.1 Other Names: Paraplatin®

8.3.2 Classification: Carboplatin (carboplatin injection) (platinum, diammine[1,1-cyclobutanedicarboxylato(2-)-O,O']-, (SP-4-2)) is platinum coordination compound, used as an anti-neoplastic agent. It is a second-generation tetravalent organic platinum compound. It is a crystalline powder with the molecular formula of C₆H₁₂N₂O₄Pt and a molecular weight of 371.25. It is soluble in water at a rate of approximately 14 mg/mL, and the pH of a 1% solution is 5 to 7. It is virtually insoluble in ethanol, acetone, and dimethylacetamide.

- 8.3.3 Mode of Action: Like cisplatin, carboplatin binds to DNA, thereby inhibiting DNA synthesis, in a cell cycle nonspecific manner. Carboplatin must first undergo activation to produce antineoplastic activity. Bidentate carboxylate ligands of carboplatin are displaced by water forming (aquation) positively charged platinum complexes which bind to nucleophilic sites in DNA, such as the O-6 position on guanine. Carboplatin produces predominantly interstrand DNA crosslinks rather than DNA-protein crosslinks. Intrastrand crosslinks result from the formation of adducts between the activated platinum complexes of the drug and the N-7 atom (not exclusively) atom on guanine to produce 1,2 intrastrand links between adjacent guanine molecules, between neighboring guanine and adenosine molecules, or between neighboring guanine molecules. Interstrand cross-linking within the DNA helix also occurs. Platinum adducts may inhibit DNA replication, transcription and ultimately cell division.
- 8.3.4 Storage and Stability: Store intact vials at room temperature at 25°C (77°F); excursions permitted to 15°C to 30°C (59°F to 86°F). Protect from light. Further dilution to a concentration as low as 0.5 mg/mL is stable at room temperature (25°C) for 8 hours in NS or D₅W. Stability has also been demonstrated for dilutions in D₅W in PVC bags at room temperature for 9 days; however, the manufacturer recommends use within 8 hours due to lack of preservative. Multidose vials are stable for up to 14 days after opening when stored at 25°C (77°F) following multiple needle entries.
- 8.3.5 Dose Specifics: Carboplatin will be administered at AUC 6 IV on day 1 every 21 days, for a total of 4 doses (3 week-cycles).
- Calvert Formula for Carboplatin (AUC) Dosing**
- Total dose (mg) = target AUC (in mg/mL/minute) * [GFR (in L/minute) + 25]
- For the purposes of this protocol, the GFR is considered to be equivalent to the creatinine clearance.
- Glomerular Filtration Rate (GFR) Estimation: Calculated creatinine clearance of ≥ 50 cc/min using the Cockcroft-Gault formula:
- Males:
$$\frac{140 - \text{Age in years} \times \text{Actual Body Weight in kg}}{72 \times \text{Serum Creatinine (mg/dL)}}$$
- Females: Estimated creatinine clearance for males × 0.85
- With the Calvert formula, the total (final) dose of carboplatin is calculated in mg, not mg/m².
- 8.3.6 Preparation: Manufacturer's labeling states solution can be further diluted to concentrations as low as 0.5 mg/mL in NS or D₅W; however, most clinicians generally dilute dose in either 100 mL or 250 mL of NS or D₅W. Concentrations used for desensitization vary based on protocol. Hazardous agent; use appropriate precautions for handling and disposal. Needles or I.V. administration sets that contain aluminum should not be used in the preparation or administration of carboplatin; aluminum can react with carboplatin resulting in precipitate formation and loss of potency.

- 8.3.7 Route of Administration: Carboplatin will be administered as an intravenous infusion.
- 8.3.8 Incompatibilities: Amphotericin B chloesteryl sulfate complex. Aluminum reacts with carboplatin causing precipitate formation and loss of potency; therefore, needles or intravenous sets containing aluminum parts that may come in contact with the drug must NOT be used for the preparation or administration of carboplatin.
- 8.3.9 Availability: Carboplatin (Bristol-Myers Oncology Division) is commercially available in 50, 150, and 450 mg vials.
- 8.3.10 Side Effects:
- 8.3.10.1 Hematologic: Thrombocytopenia, neutropenia, leukopenia, more pronounced in patients with compromised renal function and heavily pretreated patients; may be cumulative.
- 8.3.10.2 Gastrointestinal: Nausea and vomiting, treatable with moderate doses of antiemetics.
- 8.3.10.3 Dermatologic: Rash, urticaria.
- 8.3.10.4 Hepatic: Abnormal liver function tests, usually reversible with standard doses.
- 8.3.10.5 Neurologic: rarely Peripheral neuropathy.
- 8.3.10.6 Renal: Elevations in serum creatinine, BUN; electrolyte loss (Na, Mg, K, Ca).
- 8.3.10.7 Other: Pain, asthenia.
- 8.3.11 Nursing/Patient Implications
- Monitor CBC and platelet count; nadir occurs at approximately day 21 with recovery by day 28-30.
 - Premedicate with antiemetics - evaluate effectiveness.
 - Monitor fluid status - maintain adequate hydration.
 - Assess skin/mucous membranes.
 - Assess for signs of peripheral neuropathy - coordination, sensory loss.
- 8.3.12 References
- Calvert AH, et al. Carboplatin dosage: Prospective evaluation of a simple formula based on renal function. *J Clin Oncol* 1989; 7: 1748-1756.
 - Christian MC. Carboplatin. In: *Principles and Practice of Oncology*, PPO Updates 1989; 3(11): 1-16.

Rev. 6/16
Rev. 9/17
Rev. Add7

9. Statistical Considerations

Three changes are made to the study design in the Amendment #7:

- Basal-like subtype is no longer a stratification factor: Current data (ongoing monitoring) suggest that > 75% of the residual tumors tested thus far are basal subtype. Removing basal-like subtype as a stratification factor will speed up randomization and therefore will improve accrual, also allowing investigators who wish to pursue RT *after* chemotherapy completion to do so (this is particularly important for patients that wish to subsequently enroll in the phase III S1418 protocol). Patients will be randomized to arm B or arm C as long as meeting all eligibility criteria listed in Section 3 and the EA Operations Office receives confirmation of receipt of tumor tissue from EA CBPF. The basal-like subtype status will be identified after randomization, and some patients may have assay failure and their basal-like subtype status will be unknown. We expect about 7% of patients will have assay failure based on data available as of June 24, 2019 (24 out of 365 patients screened have had assay failure). This subgroup of patients with unknown disease subtype will be randomized to arm B or arm C, and they will be analyzed separately from patients with known disease subtypes (basal-like vs. non-basal like) as an exploratory objective of the study. The total sample size is updated (775 vs 750) to reflect the impact of removing basal-like subtype from the stratification factor list (i.e., about 7% of patients randomized will have assay failure) and the observed slightly higher proportion of basal-like disease in the patients (observed vs expected: 78% vs 75%).
- The futility monitoring rule based on Jennison and Turnbull repeated confidence interval (RCI) method is changed to be more conservative: The rule now is that if the lower boundary of the two-sided 95% RCI for the observed hazard ratio is greater than 0.754 (i.e., the alternative hypothesis) for arm B/arm C and the conditional power of rejecting $HR \geq 1.154$ (H_0) when $HR = 0.754$ (H_a) is less than 10%, then the trial would be stopped due to futility.
- Correlative biomarker blood studies about CTC (secondary correlative objective) added to the protocol.

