5.1.1 ARM B

Cisplatin 75 mg/m², IV infusion per institutional guidelines, day 1 every 3 weeks for a total of 4 cycles (12 weeks)

OR

Carboplatin AUC 6, IV infusion per institutional guidelines, day 1 every 3 weeks for a total of 4 cycles (12 weeks)

NOTE: CALVERT FORMULA FOR CARBOPLATIN DOSING:

Total Dose (mg) = (target AUC) x (GFR + 25)

For the purposes of this protocol, the GFR is considered to be equivalent to the creatinine clearance.

Glomerular Filtration Rate (GFR) Estimation: Calculated creatinine clearance of ≥ 50 cc/min using the Cockcroft-Gault formula:

Males:
$$\frac{(140 - \text{Age in years}) \times \text{Actual Body Weight in kg}}{72 \times \text{Serum Creatinine (mg/dL)}}$$

Females: Estimated creatinine clearance for females $\times 0.85$

With the Calvert formula, the total (final) dose of carboplatin is calculated in mg, not mg/m².

NOTE: Carboplatin maximum dose is based on a GFR estimate that is capped at 125 mL/min for patients with normal renal function. Based on Calvert formula, the recommended maximum AUC- based carboplatin dose is (or not to exceed or cap at):

AUC 6 \rightarrow 900 mg (max)

AUC 5 \rightarrow 750 mg (max)

AUC 4 \rightarrow 600 mg (max)

NOTE: Choice of platinum agent will be per treating physician discretion. Once a platinum agent is picked, no changes are allowed.

NOTE: In case of an event that causes a patient to reschedule appointments, treatment cycles should be no less than 19 days apart.

NOTE: All patients (on both arms) will be followed for development of recurrences, second primary cancer and survival based on standard ECOG-ACRIN following schedules (see Section [7](#) for details).

Rev. Add7
Rev. Add8

Rev. 9/17
Rev. Add#5

5.1.2 **ARM C**

Capecitabine 1,000 mg/m², PO twice daily, on days 1 - 14 every 3 weeks for a total of 6 cycles (18 weeks)

NOTE: In case of an event that causes a patient to reschedule appointments, treatment cycles should be no less than 19 days apart.

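### Section 8.3.5 labels GFR in L/minute in the carboplatin formula, which conflicts with the cc/min line below it and with the units and maximum doses in 5.1.1

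*Combined protocol and SAP*

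**What the plan says.** Carboplatin is one of the two platinum options in Arm B: "Carboplatin AUC 6, IV infusion per institutional guidelines, day 1 every 3 weeks for a total of 4 cycles (12 weeks". The dosing formula appears twice.

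- **Section 5.1.1** gives "Total Dose (mg) = (target AUC) x (GFR + 25", with no unit inside the formula. The unit comes from the surrounding lines. GFR is equated with creatinine clearance, estimated as "Glomerular Filtration Rate (GFR) Estimation: Calculated creatinine clearance of ≥ 50 cc/min using the Cockcroft-Gault formula", and a note adds that "Carboplatin maximum dose is based on a GFR estimate that is capped at 125 mL/min for patients with normal renal function". The listed maxima are 900 mg (AUC 6), 750 mg (AUC 5) and 600 mg (AUC 4).
- **Section 8.3.5**, under dose specifics, gives "Total dose (mg) = target AUC (in mg/mL/minute) * [GFR (in L/minute) + 25". It then equates GFR with creatinine clearance and repeats the same estimation line in cc/min. It does not repeat the cap or the maximum-dose list.

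The line for women also differs. Section 5.1.1 multiplies by 0.85 the "Estimated creatinine clearance for females", as do the eligibility criteria in 3.1.8.4 and 3.2.8.5. Section 8.3.5 multiplies by 0.85 the "Estimated creatinine clearance for males".

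**The concern.** Both sections are current text, and both are operative dosing instructions for a cytotoxic drug in the experimental arm. Section 8.3.5 contradicts itself, with L/minute in the formula and cc/min below it. It also contradicts 5.1.1. The formula adds a fixed 25 to GFR, so changing the unit of GFR without changing the 25 alters the dose greatly. A reader working from Section 8 alone has no maximum-dose list there to check the result against.

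The wording on women is a lesser matter, but the line is used often: section 9.7 expects 768 of 775 patients to be female.

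**Working it through.** **Inputs**

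- Formula, both sections: dose = AUC × (GFR + 25).
- Target AUC 6, with 5 and 4 as the other listed levels (5.1.1).
- GFR from 50 cc/min, the value in the estimation line, to the 125 mL/min cap (5.1.1). 1 cc/min is 1 mL/min.
- Literal reading of 8.3.5: the GFR number in mL/min is divided by 1,000 and the 25 is left as printed.

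**Step 1. Reproduce the plan's own figures.** At the cap, with GFR in mL/min:

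- 6 × (125 + 25) = 900 mg
- 5 × (125 + 25) = 750 mg
- 4 × (125 + 25) = 600 mg

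These equal the maxima in 5.1.1. With GFR in L/minute:

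- 6 × (0.125 + 25) = 150.75 mg
- 5 × (0.125 + 25) = 125.6 mg
- 4 × (0.125 + 25) = 100.5 mg

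The list therefore agrees with mL/min and not with the label in 8.3.5.

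**Step 2. Size of the gap at AUC 6.**

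| GFR (mL/min) | Number in mL/min | Number in L/min | Ratio |
|---|---|---|---|
| 50 | 6 × 75 = 450 mg | 6 × 25.050 = 150.3 mg | 2.99 |
| 75 | 6 × 100 = 600 mg | 6 × 25.075 = 150.45 mg | 3.99 |
| 100 | 6 × 125 = 750 mg | 6 × 25.100 = 150.6 mg | 4.98 |
| 125 (cap) | 6 × 150 = 900 mg | 6 × 25.125 = 150.75 mg | 5.97 |

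Under the literal label the dose moves by only 0.45 mg over this whole range. In mL/min it doubles.

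**Step 3. Female factor.** Let M be the value from the one printed equation, labelled for males. Applying 0.85 once gives 0.85 × M. Applying it twice gives 0.85 × 0.85 × M = 0.7225 × M. At AUC 6, in mL/min:

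| M | Once | Twice | Once ÷ twice |
|---|---|---|---|
| 70 | 6 × (59.5 + 25) = 507 mg | 6 × (50.575 + 25) = 453.45 mg | 1.118 |
| 100 | 6 × (85 + 25) = 660 mg | 6 × (72.25 + 25) = 583.5 mg | 1.131 |
| 147.06 | 6 × (125 + 25) = 900 mg | 6 × (106.25 + 25) = 787.5 mg | 1.143 |

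The single-factor dose is 12% to 14% higher than the double-factor dose. Sections 3.1.8.4 and 3.2.8.5 require a clearance above 50 mL/min, so the double reading could also change eligibility. At M = 65, one application gives 55.25 and two give 46.96.

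**The case against.** The strongest reply is that 8.3.5 does not end at the formula. It equates GFR with a creatinine clearance expressed in cc/min and never tells the reader to divide by 1,000. Followed step by step, it puts 100 into the formula for a clearance of 100 and gives 750 mg, as 5.1.1 does. A literal application would also show itself, because the dose would hardly depend on renal function.

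This stands against a stronger claim that a reader might infer: that the two sections, as procedures, prescribe doses up to sixfold apart. The documents do not support that. The gap needs a conversion that only the unit label implies, and sixfold is the extreme at the cap. The reply does not remove the contradiction, since a unit printed inside a dosing formula is part of the instruction.

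On the female factor, only one base equation is printed, so the natural quantity to multiply is that equation's result, as 8.3.5 says outright. Nothing in 5.1.1 directs a second application. This objection largely stands: the difference in wording is real but minor, and it adds nothing to the three- to sixfold figure.

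A reader might also infer that the non-inferiority comparison is distorted. That would require actual misdosing, and only among Arm B patients given carboplatin rather than cisplatin. The documents neither show nor quantify any.

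**Conclusion.** The point holds as an internal contradiction in a dosing instruction. The L/minute label in 8.3.5 conflicts with the cc/min line in the same section, and with the cc/min estimate, the 125 mL/min cap and the maximum-dose list in 5.1.1.

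Its size is conditional. The three- to sixfold difference applies over 50 to 125 mL/min at AUC 6, and only if the label is taken literally with the 25 unchanged. The 12% to 14% for the female factor applies only under a double-application reading. The case for correction is clarity and patient safety at almost no cost. It does not rest on any demonstrated effect on patients or on the trial's result.

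**What to change.** Reconcile 5.1.1 with 8.3.5, including the estimation lines below the formula in 8.3.5. One formula, one stated GFR unit and one statement of the female factor should appear in both places. Bring the matching female-factor wording in 3.1.8.4 and 3.2.8.5 into line. Whatever text the sponsor keeps, the formula, the clearance unit, the cap and the maximum-dose list should agree arithmetically. Which text stands is for the sponsor to decide; this review proposes no dose.

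The cost is a wording correction in the next addendum. Sample size, randomization and analysis are unaffected.

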9.1 Study Objectives

The primary objective of this multi-institutional, open-label, randomized phase III study is to compare the two treatment arms, platinum and capecitabine, with respect to invasive disease-free survival (IDFS) in patients with triple-negative breast cancer (TNBC) treated with taxane +/- anthracycline-based neoadjuvant chemotherapy (NAC) who do not achieve a pathologic complete response (pCR) with a residual disease of more than 1.0 cm and with basal-like gene expression via PAM50 analysis by digital mRNA quantitation (NanoString) in the residual surgical specimen. IDFS is the primary endpoint, which is defined to be time from randomization to the earliest of documented disease recurrence (local, regional and/or distant), invasive contralateral breast cancer, invasive any other second primary cancer, or death. Cases with incomplete follow up or without adequate disease evaluations will be censored at the date last documented to be free of IDFS events. Secondary endpoints include overall survival (OS), recurrence-free survival (RFS), toxicity profile and PRO. Overall survival is defined as time from randomization to death from any cause. Cases still alive will be censored at the last date of known alive.

Rev. 9/17
Rev. Add#5
Rev. Add7

9.2 Study Design

Based on the literature, the benefit of platinum agent therapy in TNBC after NAC, if any, is expected to be predominantly in the basal-like subtype. Hence, the primary population for the primary endpoint is the basal-like subtype in this trial. After screening, tumor tissue will be sent to EA CBPF for molecular profile via PAM50 analysis by digital mRNA quantitation (NanoString) in the residual surgical specimen to identify its molecular subtype. At the time when the trial was developed, we expected at least 75% of the residual post-NAC TNBC screened to fall within the basal-like subtype. Based on data available as of the 2019 Spring DSMC meeting, about 78% of the patients randomized to arms B and C fall in the basal-like subtype. We will use this proportion in the below sample size calculation. In addition, about 7% of patients screened had assay failure and their intrinsic subtype is unknown. We assume 7% of patients will have assay failure in the remaining patients as well.

After EA CBPF sending the confirmation of receipt of tumor tissue to EA Operations Office, all eligible patients will then be randomized according to the permuted block algorithm with a 1:1 randomization ratio to platinum and capecitabine arms. Stratification factors include 1) clinical stage at diagnosis (II or III), 2) residual cancer burden after NAC (1~3 cm or > 3 cm), 3) planned platinum agent (cisplatin or carboplatin), 4) anthracycline exposure in the neoadjuvant setting (yes or no), and 5) administration of radiotherapy (yes or no).

Since platinum is considered less toxic than capecitabine and also platinum is expected to be better than capecitabine on improvement of IDFS in patients with basal-like TNBC, a non-inferiority design with superiority alternative (a hybrid design³³ is preferred for this trial). The primary analysis for the primary endpoint will test the null hypothesis of inferiority of platinum. The sample size would be calculated based on a modest superiority alternative hypothesis. If the hypothesis of inferiority of platinum is rejected in the primary analysis, the secondary hypothesis of no difference vs. superiority of platinum will be tested. Due to the closed testing procedure, no multiple-comparison adjustment is required for the two hypothesis tests³⁴

Based on the accrual rate of the CALGB 40603 trial (NCT00861705, accrued 445 patients from 6/2010 to 8/2012), we anticipate an accrual rate of approximately 16 TNBC patients ($16 \times 0.93 \times 0.78 = 12$ patients with basal-like subtype) per month in our study.

9.2.1 Non-inferiority test of platinum

9.2.1.1 Sample Size and Accrual

Based on the review (by Von Minckwicz et al.(5)) of patients with TNBC (basal-like and non-basal-like) that do not achieve a pCR after neoadjuvant chemotherapy, the outcome contingent on tumor size in the residual disease show no difference between patients with pT1 and pT2; i.e. 50% of those patients recur in ~ 60 months. Of note, that would support the reasoning behind allowing patients with residual tumors ≥ 1 cm. The ones with pT3 and pT4 mimic the cohort of patients with basal-like TNBC in the analysis by Balko et al.(8) ; where 50% of them recur in 18 months. The patients with pT3 and pT4 represented ~ 20% of the

whole number of patients (in the review by Von Minckwicz et al.(5)) that did not achieve a pCR. We would expect that 20% of the patients that would potentially be accrued in our current trial would have a median IDFS of ~ 18 months and 80% would have a median DFS of ~60 months. Therefore, it would be reasonable to assume that a conservative estimate of the actual median DFS would be 48 months (i.e., 4-year DFS rate of 50%) for the study patients if receiving no chemotherapy after surgery, with a median OS of 60 months (i.e., 5-year OS rate of 50%). Based on the CREATE-X trial, the 4-year DFS rate was 67% in the 296 TNBC patients when receiving capecitabine (HR=0.58, 95% CI 0.39 – 0.87). Therefore, a conservative estimate of the 4-year IDFS rate would be 67% ($0.5^{0.58}=0.67$) for the capecitabine arm in patients with basal-like TNBC disease in this trial.

The null hypothesis for testing non-inferiority of platinum is defined as that the hazard ratio (HR) for platinum/capecitabine ≥ 1.154 (i.e., HR of 1.154 is used as the non-inferiority margin). This corresponds to a 4-year IDFS rate of $\leq 63\%$ on platinum if the 4-year IDFS rate is 67% on capecitabine arm. With a total accrual of 562 patients (281 on each arm) and full information of 196 IDFS events, this non-inferiority test would have about 83% power, with a one-sided 0.025 significance level, to reject the null hypothesis of inferiority of platinum under the alternative hypothesis of HR=0.754 for platinum/capecitabine, i.e., the 4-year IDFS rate for platinum is expected to be 73.9%.

With an average annual accrual rate of 144 patients with basal-like TNBC, about 3.9 years of accrual will be needed with an additional 3 years of follow up to reach the expected number of IDFS failures. The final analysis for IDFS comparison in the basal-like TNBC patients is expected to be conducted at about 7.5 years (3.9 years of accrual + 3 years of follow up + 0.5 years of data collection and cleaning) after study activation.

We expect at least 78% of the residual post-NAC TNBC screened to fall within the basal-like subtype within the patients with successful assay, and about 7% of patients will have assay failure. Hence, at least 775 patients ($=562/0.78/0.93$) with residual TNBC at the time of surgery will be enrolled to obtain the 562 patients with basal-like TNBC.

9.2.1.2 Interim analysis plan

The study will be monitored by the ECOG-ACRIN Data and Safety Monitoring Committee (DSMC) according to the principals of group-sequential methods. The first interim analysis will be performed at the first DSMC meeting when

Rev. Add7

at least 25% of the total information has been reported. Since 196 IDFS failures are required as the total information under the alternative hypothesis, the first interim analysis is estimated to take place after 49 IDFS failures have occurred, which corresponds to 2.9 years after activation of the study in calendar time, under the accrual and failure rate assumptions mentioned above. Interim analysis will be performed for each subsequent DSMC meeting until either the criteria for early stopping (described below) are met or the total planned number of IDFS failures has been reported. In total, this design is expected to incorporate 8 interim analyses and one final analysis for IDFS comparisons.

The Jennison and Turnbull repeated confidence interval (RCI) methodology³⁵ will be used to monitor the trial in favor of non-inferiority. At each interim analysis, a two-sided 95% RCI on the log hazard ratio (logHR) for platinum/capecitabine will be computed using partial likelihood estimation method, and the critical value for each interim analysis (see Table 1) will be based on Lan-DeMets error spending rate function⁽⁴³⁾ corresponding to the truncated version of O'Brien-Fleming boundaries⁽⁴⁴⁾ with an overall one-sided type I error rate of 0.025. The partial likelihood estimator of logHR and its standard error will be derived from stratified Cox proportional hazard model, where the patients will be stratified using the same factors as the randomization (i.e., clinical stage at diagnosis, residual cancer burden after NAC, planned platinum agent, anthracycline exposure in the neoadjuvant setting, and administration of radiotherapy). The confidence interval for the HR will be reported by exponentiating the logHR intervals. When the upper confidence limit for the HR is less than 1.154 (the pre-defined non-inferiority margin) at any interim analysis or final analysis, then the null hypothesis of inferiority of platinum will be rejected, and we would conclude that the platinum therapy is non-inferior to capecitabine in terms of IDFS. The primary hypothesis of the trial (i.e., non-inferiority of platinum) is then answered, and superiority test of platinum (i.e., secondary hypothesis of the trial) would be then performed (see Section [9.2.2](#)). If this occurs at an interim analysis, accrual to the study will continue to allow a definitive answer to the secondary hypothesis test (superiority of platinum), i.e., the rejection of null hypothesis for the non-inferiority test of platinum will not result in early termination of the trial.

Table 1 shows expected timing of interim analyses and critical values for early stopping monitoring under the alternative hypothesis of HR=0.754 for platinum/capecitabine. Because interim analyses are timed to coincide with the semi-annual ECOG-ACRIN DSMC

meetings, these boundaries may change depending on the number of observed IDFS failures at that time. Also, because of delays in data submission and processing, it is likely that actual analysis times will be 6-12 months later.

Table 1: Expected timing of interim analyses and critical values under the alternative hypothesis of HR=0.754 (i.e., 4-year IDFS rate of 67% on capecitabine vs. 73.9% on platinum)

| Repeated analysis | Time from study activation (years) | Information time (%) | Number of Failures under alternative | Upper boundary (critical value for two-sided 95% RCIs) |
|-------------------|------------------------------------|----------------------|--------------------------------------|--|
| 1 | 2.9 | 0.25 | 49 | 3.2905 |
| 2 | 3.4 | 0.34 | 67 | 3.2905 |
| 3 | 3.9 | 0.44 | 87 | 3.2905 |
| 4 | 4.4 | 0.55 | 107 | 2.9084 |
| 5 | 4.9 | 0.65 | 126 | 2.6218 |
| 6 | 5.4 | 0.74 | 145 | 2.4376 |
| 7 | 5.9 | 0.83 | 162 | 2.2980 |
| 8 | 6.4 | 0.92 | 179 | 2.1870 |
| Final | 6.9 | 1.00 | 196 | 2.0962 |

In addition to efficacy monitoring for the non-inferiority test, the trial will be monitored to allow early stopping for inferiority of platinum based on conditional power and the above RCI methods. At each interim analysis, the conditional power of the log rank test for the primary comparison at a one-sided type I error rate of 0.025 will be computed using simulation, and if the conditional power of the assigned treatment analysis is < 10% and the lower boundary of the above two-sided 95% RCI is greater than 0.754 for arm B/arm C (the alternative hypothesis), then the trial would be stopped due to futility unless there is other supporting evidence for non-inferiority of platinum at the time. We would conclude that the trial fail to reject the null hypothesis of inferiority of platinum, and platinum is inferior to capecitabine. If the conditional power is > 10% or the lower boundary of the 95% RCI is below 0.754, the trial would continue.

